7.5.7 Laboratory Assessments

Subjects who experience disease progression (PSA or radiographically) before the end of 12 months should complete laboratory assessments at the Progression Visit as outlined in the Study Schedule. During treatment, laboratory assessments include the following:

- Serum PSA level measured by ultrasensitive assay at the end of each month
- Complete blood count including differential and platelet count at the end of Months 3, 6, 9, and 12 of protocol therapy.
- Total bilirubin, alkaline phosphatase, AST, ALT at the end of Months 3, 6, 9, and 12.
- TSH at the end of Months 3, 6, 9, and 12.
- Fasting glucose, fasting lipid panel (total cholesterol, LDL, HDL, triglyceride), and hemoglobin A1C at the end of Months 3, 6, 9, and 12.
- Peripheral blood collection for measurement of serum testosterone, DHT, estradiol, and fasting serum insulin levels at the end of Months 3, 6, 9, and 12 (see Appendix 6 for collection, processing, and shipping instructions).
- Peripheral blood and urine collection for banking of, serum, plasma, and urine at the end of Months 3, 6, 9, and 12 of protocol therapy (optional). See Appendix 6 for procedures to ensure subject confidentiality and instructions on collection, processing, shipping of samples.
- Whole blood collected for PAXgene analysis (optional) on Day 1 and end of Month 12

7.5.8 Radiographic Assessments

A whole body nuclear bone scan, along with cross-sectional imaging of the abdomen/pelvis (CT or MRI) will be obtained as prompted by signs and symptoms of metastatic disease and at the time of PSA progression. DEXA scan measuring BMD at the femoral neck, and lumbar spine will be obtained after 12 months of protocol therapy or at the time of PSA or radiographic progression (if occurs before Month 12, see Progression Visit in Study Schedule).

Subjects who are intolerant of IV CT contrast agents may have CT scans performed with oral contrast or without, as long as method is identical each time new scans are done.

There will be no central reading of the scans and radiographic progression will be based upon investigator assessment.

7.6 STUDY PERIOD II: OFF-THERAPY OBSERVATION PERIOD (MONTHS 13 TO 24)

Subjects without progressive disease (by PSA or radiographic) after 12 months of protocol therapy will stop protocol therapy and enter the Off-therapy Observation Period from Month 13 to Month 24. Continuation of hormonal therapy or initiation of any other of anti-cancer therapy in the absence of PSA or radiographic progression will be considered non-protocol therapy and will result in study removal. Use of concomitant medications, which may affect serum PSA will not be permitted (see Section 7.5.4).

Subjects who develop either PSA or radiographic progression during the Off-therapy Observation Period will have a Progression Visit, and be treated as per individual investigator discretion. Efforts will be made to ensure that subjects who develop progressive disease (PSA or radiographic) or discontinue in the absence of progressive disease before 24 months still complete QOL scales after 24 months as prespecified in the study protocol.

7.6.1 Safety Assessment

Subjects will be assessed for adverse events at clinic visits at the end of every 2 months during the Off-therapy Observation Period.

7.6.2 QOL

The FACT-P, EORTC QLQ-C30/QLQ-PR25, and SHIM questionnaires will be completed at the time of progression (PSA or radiographic) or after 24 months.

7.6.3 Laboratory Assessments

Subjects who experience disease progression (PSA or radiographic) before the end of 24 months should complete laboratory assessments at the Progression Visit as outlined in the Study Schedule. During the Off-therapy Follow up Period laboratory assessments include the following:

- Serum PSA level at the end of every 2 months (see Section 10.6).
- Peripheral blood collection for measurement of serum testosterone levels at the end of every 2 months (see Appendix 6 for collection, processing, and shipping instructions).
- Fasting glucose, fasting lipid panel (total cholesterol, LDL, HDL, triglyceride), and hemoglobin A1C at the end of Months 18 and 24.
- Peripheral blood collection for measurement of fasting serum insulin at the end of Months 18 and 24 (see Appendix 6).

7.6.4 Radiographic Assessment

A whole body nuclear bone scan, along with cross-sectional imaging of the abdomen/pelvis (CT or MRI; with IV contrast per individual investigator discretion), will be obtained as prompted by signs and symptoms of metastatic disease and at the time of PSA progression.

Subjects who are intolerant of IV CT contrast agents may have CT scans performed with oral contrast or without, as long as method is identical each time new scans are done

There will be no central reading of the scans and radiographic progression will be based upon investigator assessment.

7.7 FOLLOW UP PERIOD (MONTH 25+)

Subjects without progressive disease (PSA or radiographic) at end of 24 months will enter a Follow-up Period. During this period, subjects will be followed by history and physical exam, serum PSA, and testosterone levels every 3 months. Subjects who develop PSA or radiographic

progression, or initiate non-protocol therapy will be removed from study and treated as per individual investigator discretion.

If no progressive disease occurred during Months 1 to 24 and it occurs during the Follow-up Period, whole blood RNA and plasma sample collections for biomarker testing should be collected from subjects who consented to this optional sample collection (see Section 7.2, Appendix 6).

7.8 REASONS FOR STUDY DISCONTINUATION

Subjects will discontinue study protocol treatment for the following reasons, whichever comes soonest:

- PSA progression, defined as an increase in PSA to > 50% of the baseline value or an increase of > 2 ng/mL above the nadir, whichever is higher, confirmed by repeat measurement at least 2 weeks later.
- Radiographic progression, defined as the detection of new metastasis on either bone scan or cross-sectional imaging (CT or MRI).
- Subject or treating physician decision
- Unacceptable toxicity
- Non-protocol therapy

Efforts will be made to ensure that subjects who discontinue in the absence of progressive disease (PSA or radiographic) enter the Off-therapy Observation Period or the Follow-up Period (see also Sections 7.5, 7.6 and 7.7).

8 STUDY DRUG INFORMATION

8.1 ARN-509

Drug Substance: ARN-509 drug substance is an almost white to slightly brown powder

Chemical Name: (4-[7-(6-cyano-5-trifluoromethylpyridin-3-yl)-8-oxo-6-thioxo-5,7-diazaspiro[3.4]oct-5-yl]-2-fluoro-*N*-methylbenzamide)

Molecular Formula: C₂₁H₁₅F₄N₅O₂S

Molecular Weight: 477.44

Formulation: The ARN-509 tablet supplied for this study contains 60 mg of JNJ-56021927. It will be manufactured and provided under the responsibility of the Sponsor. Refer to the Investigator's Brochure for a list of excipients.

Packaging, Storage, and Labeling: The ARN-509 60-mg tablets will be packaged in 120-count, 160 cc high-density polyethylene (HDPE) bottles with child-resistant caps. Study drug labels will contain information to meet the applicable regulatory requirements

Dose and Administration

ARN-509 will be administered orally on a continuous daily dosing regimen at a dose of 240 mg per day (4 x 60-mg tablets) with or without food.

The switch to tablets for subjects who are receiving softgel capsules will occur at the start of the next cycle (onsite visit). Each softgel capsule contains 30 mg of active drug, and each tablet contains 60 mg of active drug. The conversion from the softgel capsules to the tablet formulation is **2:1** (Table 1).

Table 1 Softgel Capsule to Tablet Conversion

Dose	Number of Softgel Capsules	Number of Tablets
240 mg	8	4
180 mg	6	3
120 mg	4	2

Drug Supply: Study drug will be provided free of charge to subjects enrolled on this study by the company Sponsor. ARN-509 is to be ordered directly from a designee indicated by the study Sponsor.

Dispensing of Drug: Sufficient study drug for the next cycle of therapy will be provided to subjects randomized to one of the two ARN-509 treatment arms at each monthly study visit.

Inventory and Control: The ARN-509 used for this study must be maintained under adequate security and stored in the pharmacy at the study site until dispensing or their destruction at each study site's investigational pharmacy. Investigators may not supply study medication to any person not enrolled in this study or to any person not named as a sub-investigator. In addition,

the investigator must maintain an accurate, running inventory of all drug supplies received and dispensed during conduct of the study.

Return of Clinical Supplies: Upon completion or termination of the study, all used and unused original study drug bottles, whether empty or containing study drug, should be destroyed at each study site's investigational pharmacy (or site's authorized destruction unit) following their site-specific procedure on drug destruction after the study Sponsor approves the drug destruction policy at the site. Any return shipments must provide proof of delivery, and will be accompanied by the Drug Accountability Form and a memo noting the number of bottles and quantity of study drug being returned in the site's drug accountability records. Drug will not be returned to the Sponsor.

8.2 LHRH AGONIST

Choice of specific LHRHa to be used in this study will be per investigator discretion/site practice guidelines. Options include Eligard[®], Lupron Depot[®], Zoladex[®], or Trelstar[®]. Dosing schedule will be per individual investigator discretion.

Route of Administration: The LHRHa injections will be delivered either subcutaneously (Eligard[®], Zoladex[®]) or intramuscularly (Lupron Depot[®] or Trelstar[®]) by a trained health care provider while on protocol therapy.

Drug Supply: The use of LHRHa in this disease setting is considered standard of care and as such will be billed to the subject's medical insurance.

Dispensing of Drug: Subjects will receive a LHRHa injection either subcutaneously or intramuscularly depending on the specific drug formulation.

9 DOSAGE MODIFICATIONS/TOXICITY

9.1 TOXICITY

Toxicities and Adverse Events will be assessed during each monthly clinic visit using the NCI-CTCAE Version 4.03. Because CTEP has standardized the CTCAE, the NCI does not require the inclusion of the CTCAE within this protocol document. However, all appropriate treatment areas will have access to a copy of the CTCAE Version 4.03. A copy can be downloaded from the CTEP home page: <http://ctep.cancer.gov>

9.2 DOSE MODIFICATIONS FOR ARN-509

Inpatient dose interruptions or reductions will be permitted provided that study discontinuation criteria have not been met (Section 7.8).

- Subjects experiencing seizure of any grade or Grade 4 neurotoxicity will have protocol therapy permanently discontinued.
- For subjects experiencing Grades 1-2 treatment-related adverse events, short treatment breaks can be instituted as per the discretion of the Investigator until the severity of the toxicity decreases to Grade 1 or returns to baseline. If toxicity recurs, dose reductions to the next lower dose level will be allowed as per the discretion of the Investigator.
- For subjects experiencing Grade ≥ 3 treatment-related adverse events other than seizure, Grade 4 neurotoxicity or life threatening toxicity, study drug should be held until the severity of the toxicity decreases to Grade 1 or returns to baseline. If toxicity recurs at Grade 3 or higher, the dose of ARN-509 should be reduced to the next lower dose level. A maximum of 2 dose level reductions will be allowed (Table 2).
- Any subject requiring > 28 days delay in treatment due to AEs may meet one of the criteria for study treatment discontinuation (see Section 7.8), which must be discussed with Sponsor.

Table 2 ARN-509 Dose Levels

Total Daily Dose	Number of 60-mg Tablets (QD)
240 mg	4
180 mg	3
120 mg	2

Doses reduced for study treatment-related toxicities should generally not be re-escalated, however, re-escalation back to the previous dose level may be permitted in consultation with the Sponsor.

9.3 DOSE MODIFICATIONS FOR LHRHA

There will be no mandated dose reductions or delays for LHRHa therapy due to adverse events that are typically attributed to ADT, including anemia, hot flashes, gynecomastia, fatigue, mood changes, decreased libido, erectile dysfunction, and weight gain. Unanticipated adverse events that are not included in the above list, that the investigator attributes to LHRHa therapy will be

recorded, and if Grade 3 or higher in severity for a duration of more than 4 weeks, will lead to study discontinuation due to unacceptable toxicity and treatment as per individual investigator discretion.

10 ASSESSMENT OF INVESTIGATIONAL PRODUCT

10.1 FACT-P SCALE

The FACT-P scale [version 4.0] is a well validated metric [33] developed by Cella and colleagues, which includes a 27-item “core” quality of life measure (FACT-G) grouped into 4 subscales: physical well-being, social/family well-being, emotional well-being, and functional well-being. There are an additional 12 items specific to prostate cancer; 10 of which are prostate cancer specific physical problems. Items are rated on a 5-item Likert scale, from 0, “not at all”, to 4, “very much” (see [Appendix 1](#)). The total range of scores is from 0 – 156. Higher scores indicate higher degree of functioning and better quality of life. Internal consistency of the prostate cancer specific subscale ranged from 0.65 to 0.69, with coefficients for FACT-G subscales and aggregated scores ranging from 0.61 to 0.90. Concurrent validity was confirmed by the ability to discriminate subjects by disease stage, performance status, and baseline prostate-specific antigen (PSA) level. Sensitivity to change in performance status and PSA score over a 2-month period suggested that some subscales of the FACT-P are sensitive to meaningful clinical change [33]. Prior clinical trials have established that minimally important differences that are clinically significant and may impact treatment decisions range from 5 to 8 points depending on tumor subtype [57].

As per standard scoring guidelines for the FACT-P scale, if a subject does not answer specific items of from a subscale of the FACT-P, the weighted average of the remaining answered items will be used for scoring purposes, as long as > 50% of items are answered for that particular subscale. If there are less than 50% of items answered in a given subscale, or less than 80% of items answered overall, the FACT-P score for that particular subject will be excluded from the statistical analysis.

10.2 EORTC QLQ-C30/QLQ-PR25

The EORTC QLQ-C30 [version 3] is a well validated [34], and widely used measure of health-related quality of life among cancer patients. The EORTC QLQ-C30 consists of 30 items, which list the functioning and symptoms of cancer patients. Five multi-item function scales are scored: physical function (PF), role function (RF), emotional function (EF), social function (SF), and global health status/quality of life. Furthermore, nine single-item scales (symptoms) are scored, including fatigue, pain, dyspnea, and gastrointestinal problems. The scales are, according to the EORTC guidelines, linearly transformed: all scales range from 0 to 100, in which a higher scale score represents a higher level of functioning. With respect to the single-item scale, a higher score indicates more symptoms or problems; scores of these items will be inverted for the purposes of statistical analysis. In addition, a subscale related to prostate cancer (EORTC QLQ-PR25) will also be administered, consisting of 25 items, with the same linear transformation to a scale ranging from 0 to 100 (see [Appendix 2](#)).

10.3 SEXUAL HEALTH INVENTORY FOR MEN (SHIM)

The Sexual Health Inventory for Men (SHIM) is a well validated [38] abridged 5-item of the 15-item International Index of Erectile Function, which has been extensively studied in men with erectile dysfunction due to various etiologies, including prostate cancer-related therapies. It consists of 5 items pertaining to sexual functioning, with scores ranging from 0-5 for most items.

Higher scores indicate higher level of sexual function and less erectile dysfunction (see [Appendix 3](#)).

10.4 ADMINISTRATION OF QOL QUESTIONNAIRES

The aforementioned questionnaires (FACT-P, EORTC QLQ-C30/QLQ-PC25 and SHIM) will be administered to each subject according to the study schedules (see Sections 7.1 and 7.2). The questionnaires should take approximately 20-30 minutes to complete. A designated clinical research coordinator will ensure that subjects complete the questionnaires during their study visit. If a subject stops protocol therapy due to unacceptable toxicity or progressive disease, effort will be made to ensure that subjects continue to complete QOL questionnaires according to the study schedule.

10.5 METABOLIC PARAMETERS

Subjects experiencing disease progression (PSA or radiographic) during either the On-therapy Period or the Off-therapy Observation Period should complete assessments required at the Progression Visit (see Study Schedules for details).

10.5.1 Markers of Insulin Resistance

Fasting plasma glucose, fasting serum insulin, body mass index, and hemoglobin A1C will be measured according to the study schedules (See Sections 7.1 and 7.2). Subjects must be fasting for at least 12 hours prior to collection of blood for fasting glucose and insulin measurement. If the subject is not in a fasting state at the particular time point, the fasting glucose and insulin tests will be omitted from the analysis.

Peripheral blood for fasting serum insulin level determination will be collected, shipped and banked as per instructions outlined in [Appendix 6](#).

10.5.2 Fasting Lipid Panel

The fasting lipid panel (total cholesterol, LDL, HDL, and triglycerides) will be measured at according to the study schedules (see Sections 7.1 and 7.2). Subjects must be fasting for at least 12 hours prior to collection of blood for accurate measure of fasting lipid panel. If the subject is not in a fasting state at a particular study time point, the lipid panel will not be collected on that date and omitted from these exploratory statistical analyses.

10.5.3 Bone Mineral Density

DEXA scans will be completed during the On-therapy Period according to the study schedule (see Section 7.1) The mean percent change in bone mineral density as measured at the femoral neck, and lumbar spine will be compared between experimental ARN-509 containing arms and control LHRHa monotherapy arm.

10.5.4 Serum Hormone Levels

Peripheral blood for measurement of serum hormone levels, including testosterone, estradiol, and dihydrotestosterone, will be collected, banked, and shipped as outlined in [Appendix 6](#). See study schedules for timing of sample collection (Sections 7.1 and 7.2).

10.6 PSA MEASUREMENT

Serum PSA will be measured using local CLIA-certified laboratory using an ultrasensitive assay. It is preferable that each subject has serial laboratory measurements of PSA at the same laboratory while on study.

10.7 OPTIONAL SAMPLE COLLECTION FOR BANKING, RNA, AND BIOMARKER ANALYSIS

Optional samples of peripheral blood will be collected for banking of plasma, serum, and PBMCs. Archival FFPE blocks or slides, whole blood for RNA testing, and biomarker collection are also optional. Please see Appendix 6 for collection, processing, and shipping instructions). Archival FFPE blocks are preferred however slides will also be accepted. Whole blood will be collected in PAXgene tubes for RNA testing for markers previously confer resistance to ARN-509 or enzalutamide. These include androgen receptor anomalies (eg: AR amplification, ARv3/7, and ARv567), AR axis genes, and other compensatory pathway markers. See Study Schedules (Section 7) for timing of optional sample collections.

Biomarker analyses are dependent upon the availability of appropriate biomarker assays and adequate sample material. Therefore, some analyses may be deferred or not done if, for any reason, the analysis will have no scientific value. Biomarker data from this study may be compared with or combined with data obtained from prior studies.

11 PLANNED STATISTICAL METHODS

Statistical analysis will be done by the sponsor or under the authority of the sponsor. A general description of the statistical methods to be used in analyzing the data is outlined in the protocol. Details will be provided in the Statistical Analysis Plan (SAP).

11.1 DETERMINATION OF SAMPLE SIZE AND STUDY POWER

The expected mean decline in FACT-P score and within group standard deviation for the control arm treated with 12 months of LHRHa monotherapy is 4-8 and 8-12 points, respectively, based on prior studies of measuring QOL using FACT-P among men treated with ADT [32, 58, 59]. A change in total FACT score that is clinically meaningful and impacts treatment in prior studies ranges from 5-8 points depending on cancer subtype [56]. Approximately 30 subjects will be randomized to each of the 3 treatment arms for this comparison. Accounting for a dropout/questionnaire non-completion rate of 10%, this will allow for 27 evaluable subjects per study arm. For the comparison of the mean change in FACT-P score between ARN-509 monotherapy and LHRHa monotherapy, this sample size has 80% power to detect an effect size of at least 0.86, corresponding to a difference of 7.5 points in mean 12 month change in FACT-P score between treatment groups with a common standard deviation for the change in each arm of 8.7 which is similar to the reported standard deviation for LHRHa monotherapy. This is based upon a 2 group t test, using a bidirectional level of significance of 0.025 (adjusted for 2 comparisons). To test for non-inferiority in QOL with ARN-509 + LHRHa compared with LHRHa monotherapy, inferior QOL is defined as a greater than 7 point difference in mean change in FACT-P score between the treatment groups and the common standard deviation is again assumed to be 8.7. This sample size has 82% power to reject the null hypothesis of a difference in mean score and accept the alternative hypothesis of non-inferiority with an effect size of at least 0.81, using a 2 group t-test with 2-sided α of 0.025.

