11.4 METHODS FOR ANALYSIS

11.4.1 Analytic Plan for the Primary Endpoint

Change from baseline in FACT-P total scale will be analyzed using a mixed-model for repeated measures (MMRM). The model will include baseline scale, treatment, month (categorical), and treatment-by-month interaction as covariates. An unstructured variance-covariance matrix will be used to model within-subject errors, but simpler structures (eg, compound symmetry) may be used to ensure estimation convergence. Change from baseline will be estimated using least-squares means with factor levels weighted according to overall baseline sample means. Data up to 12 months will be included in the analysis and the primary time point of interest will be at 12 months.

Contrasts will be set up to compare ARN-509 monotherapy vs. LHRHa monotherapy and ARN-509 + LHRHa vs. LHRHa monotherapy. To test for non-inferiority with respect to ARN-509 + LHRHa compared with LHRHa monotherapy, inferior boundary is defined as a greater than 7 point difference in mean change in FACT-P total score.

The estimated least-squares mean (+/- SE) over time will be presented using a line plot.

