1.4 Sample Size Justification

The expected mean decline in FACT-P score and within group standard deviation for the control arm treated with 12 months of LHRHa monotherapy are 4-8 and 8-12 points, respectively, based on prior studies of measuring QOL using FACT-P among men treated with ADT [1, 2, 3]. A change in total FACT-P score that is clinically meaningful and impacts treatment in prior studies ranges from 5-8 points depending on cancer subtype [4]. Approximately 30 subjects will be randomized to each of the 3 treatment arms for this comparison. Accounting for a dropout/questionnaire non-completion rate of 10%, this will allow for 27 evaluable subjects per study arm. For the comparison of the mean change in FACT-P score between apalutamide monotherapy and LHRHa monotherapy, this sample size has 80% power to detect an effect size of at least 0.86, corresponding to a difference of 7.5 points in mean 12 month change in FACT-P

score between treatment groups with a common standard deviation for the change in each arm of 8.7 which is similar to the reported standard deviation for LHRHa monotherapy. This is based upon a 2-group t test, using a bi-directional level of significance of 0.025 (adjusted for 2 comparisons). To test for non-inferiority in QOL with apalutamide + LHRHa compared with LHRHa monotherapy, inferior QOL is defined as a greater than 7-point difference in mean change in FACT-P score between the treatment groups and the common standard deviation is again assumed to be 8.7. This sample size has 82% power to reject the null hypothesis of a difference in mean score and accept the alternative hypothesis of non-inferiority with an effect size of at least 0.81, using a 2-group t-test with 2-sided α of 0.025.

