5.1 Analysis Specification

5.1.1 Level of Significance

In general, a two-sided significance level of $\alpha = 0.05$ will be used for all hypothesis testing and all CIs will be calculated on the two-sided 95% confidence level, unless otherwise specified. Since this is a three-arm study testing two simultaneous hypotheses, $\alpha/2 = 0.025$ level of significance will be used to test each.

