5.2.1 Analytic Plan for the Primary Endpoint

Change from baseline in FACT-P total scale will be analyzed using a mixed-model for repeated measures. The model will include baseline scale, treatment, month (categorical), and treatment-by-month interaction as covariates. An unstructured variance-covariance matrix will be used to model within-subject errors, but simpler structures (eg, compound symmetry) may be used to ensure estimation convergence. Change from baseline will be estimated using least-squares means with factor levels weighted according to overall baseline sample means. Data up to 12 months will be included in the analysis and the primary time point of interest will be at 12 months. Contrasts will be set up to compare apalutamide monotherapy vs. LHRHa monotherapy and apalutamide + LHRHa vs. LHRHa monotherapy. To test for non-inferiority with respect to apalutamide + LHRHa compared with LHRHa monotherapy, inferior boundary is defined as a greater than 7-point difference in mean change in FACT-P total score. The estimated least-squares mean (+/- SE) over time will be presented using a line plot. A sensitivity analysis will be conducted by including data up to 24 months.

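### The stated 82% non-inferiority power does not follow from the printed 2-sided alpha of 0.025 (the inputs give about 74%), and the analysis sections do not name the confidence bound to set against the 7-point margin

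*Protocol*

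**What the plan says.** Protocol 11.1 plans both primary FACT-P comparisons in one paragraph. After a 10% allowance for dropout or missing questionnaires, "this will allow for 27 evaluable subjects per study arm". For superiority of ARN-509 monotherapy, with SD 8.7 and 2-sided alpha 0.025, "this sample size has 80% power to detect an effect size of at least 0.86".

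For non-inferiority of the combination, the margin is 7 points and the SD is again 8.7. The text says "This sample size has 82% power to reject the null hypothesis of a difference in mean score and accept the alternative hypothesis of non-inferiority", and continues "with an effect size of at least 0.81, using a 2 group t-test with 2-sided" alpha of 0.025. SAP 1.4 gives the same figures, including "with an effect size of at least 0.81, using a 2-group t-test with 2-sided" alpha of 0.025.

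The analysis sections state the margin only. Protocol 11.4.1 says "inferior boundary is defined as a greater than 7 point difference in mean change in FACT-P total score", and SAP 5.2.1 says "inferior boundary is defined as a greater than 7-point difference in mean change in FACT-P total score". Neither names a confidence limit or a level. SAP 5.1.1 sets a general default, "all CIs will be calculated on the two-sided 95% confidence level, unless otherwise specified", and then assigns 0.025 to each of the two primary hypotheses without saying whether that is one- or two-sided.

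**The concern.** The contradiction shows without software. With n, SD, test and alpha all the same, a standardized effect of 0.81 cannot have more power (82%) than one of 0.86 (80%). At least one printed element of the non-inferiority statement must be wrong.

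This goes beyond a planning slip because the two obvious repairs lead to different decision rules. A 2-sided 0.025 test corresponds to a two-sided 97.5% interval. A one-sided 0.025 test corresponds to the two-sided 95% interval, which is also the SAP's default. The alpha label points to the first and the power figure points towards the second. Non-inferiority is one of the two primary objectives and the study is open-label, so an unnamed bound leaves room for a choice made after the data are seen.

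**Working it through.** **Inputs (protocol 11.1, SAP 1.4).** n = 27 evaluable per arm, so df = 52. SD = 8.7. Margin = 7, so 7/8.7 = 0.805 (printed as 0.81). Two-group t-test, 2-sided alpha 0.025, which puts 0.0125 in the favourable direction. The true difference is not printed. An effect size equal to margin/SD implies that it is 0, and I assume that throughout.

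**Formula.** Noncentrality = d × √(n/2). Power = P(T > t_crit), where T is noncentral t with 2n − 2 df. For n = 27, √(27/2) = 3.674. The critical value is 2.308 at 0.0125 in one tail and 2.007 at 0.025 in one tail.

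**1. Reproduce the superiority figure.** For d = 0.86, noncentrality = 0.86 × 3.674 = 3.160 and power = 80.0%, as printed. With d = 7.5/8.7 it is 80.2%. The method is therefore the one the plan used for that comparison.

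**2. Apply the same method to non-inferiority.**

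| n per arm | Alpha | d = 7/8.7 | d = 0.81 |
|---|---|---|---|
| 27 | 2-sided 0.025 (as printed) | 74.0% | 74.6% |
| 30 (no dropout) | 2-sided 0.025 | 79.0% | 79.6% |
| 27 | one-sided 0.025 | 82.7% | 83.2% |

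The printed inputs fall about 8 points short of 82%. Dropping the 10% allowance does not close the gap under the t-test. One-sided 0.025 comes close, and rounding the effect size to 0.80 gives 82.2%. A normal approximation with all 30 per arm at 2-sided 0.025 gives 80.9% to 81.5%, but that contradicts both the printed t-test and the printed 27 evaluable.

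**3. What the unnamed bound does to the verdict.** Planning SE = 8.7 × √(2/27) = 2.368.

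- 97.5% interval: half-width 2.308 × 2.368 = 5.47; largest observed deficit that passes = 7 − 5.47 = 1.53 points.
- 95% interval: half-width 2.007 × 2.368 = 4.75; largest observed deficit that passes = 7 − 4.75 = 2.25 points.

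An observed deficit between these limits passes on one reading and fails on the other. At a true difference of 0 this happens in 82.7% − 74.0% = 8.7% of trials.

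**4. Baseline adjustment.** The planned MMRM includes the baseline score, and the documents give no correlation. If the baseline-to-change correlation r is assumed to lie between 0.3 and 0.5, the SD becomes 8.7 × √(1 − r²), and power at 2-sided 0.025 with 27 per arm is 78.3% (r = 0.3), 81.7% (r = 0.4) or 86.2% (r = 0.5).

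**The case against.** The arithmetic is hard to dispute. The stronger objections concern the decision rule and the practical effect.

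- **The rule may already be complete.** Alpha and sidedness are printed in the sample-size sections, and SAP 5.1.1 applies its 95% default only where nothing else is specified, then gives 0.025 per hypothesis. A contrast tested against a shifted null at 2-sided 0.025 needs no named interval, and its matching interval is the 97.5% one. This has force: it is the better reading of the printed alpha, and it makes naming the bound a clarification. It does not close the matter, because SAP 5.1.1 gives no sidedness for the 0.025 and the stated power fits the other reading better.
- **One-sided 0.025 is not an exact source.** It gives 82.7% or 83.2%, both of which round to 83%, and the normal approximation with 30 per arm also comes near. This stands. The documents do not show which element is wrong.
- **Little follows from the power figure itself.** The protocol abstract treats the last patient as already consented, so sample size is not at issue, and a baseline-adjusted MMRM could reach 82%. The first part is true. The second does not rescue the text, which attributes 82% to a two-group t-test. Any gain from adjustment would also raise the superiority figure, which reproduces without it.

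**Conclusion.** The point holds. On the printed inputs, planning power for non-inferiority is about 74%, against 82% stated in both documents. This is an unadjusted t-test figure at an assumed true difference of 0 and SD 8.7; the MMRM may do better by an amount the documents do not let one determine. If 2-sided 0.025 is right, the stated power is about 8 points too high. If one-sided 0.025 was meant, the power is about right and the alpha label is wrong. Alpha and sidedness are printed for the planning calculation, so the gap in the analysis sections is narrower: the bound to be compared with the 7-point margin is not named, and the default 95% interval does not match a 2-sided 0.025 test. The correction should be made, with high confidence in the arithmetic and no firm view on how the error arose.

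**What to change.** Make power, alpha and interval agree, in writing, before the primary analysis.

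**(A) Keep the printed 2-sided 0.025.** Restate the power in SAP 1.4 and protocol 11.1 as about 74%, noting that this is an unadjusted t-test figure at a true difference of 0 and that the baseline-adjusted MMRM may differ. Add to SAP 5.2.1:

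> Non-inferiority is declared if the lower limit of the two-sided 97.5% CI for combination minus LHRHa at 12 months is above −7.

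**(B) Only if the sponsor documents that one-sided 0.025 was intended.** Change 2-sided to one-sided in both sample-size sections, state about 83% power, compare the lower limit of the two-sided 95% CI with −7, and say in SAP 5.1.1 that the 0.025 for this hypothesis is one-sided.

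The documents do not say whether the primary data have been analysed. If they have, keep the printed 2-sided 0.025 and record the clarification and both intervals in the clinical study report.

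**Cost.** No extra patients or data. The decision rule needs only SAP text, because protocol section 11 leaves details to the SAP. Correcting protocol 11.1 falls under the amendment rule in protocol 15.1 (prior written IRB/IEC approval). Protocol 15.2 exempts purely logistical or administrative changes, and whether a corrected power figure qualifies is arguable. Under (A) the protocol correction can wait for the next amendment, with the difference noted in the study report. The price of (A) is a less favourable stated power. The price of (B) is a 2.5% rather than 1.25% chance of declaring non-inferiority at a true 7-point deficit. With superiority left at 2-sided 0.025, the summed favourable-direction alpha also rises from 0.0125 + 0.0125 = 0.025 to 0.0125 + 0.025 = 0.0375.
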